Middle meningeal artery embolization is a minimally invasive angiography procedure completed either under general anesthesia or conscious sedation (per preference of the performing physician) with use of fluoroscopy. Access is obtained through the femoral or radial artery and a catheter is advanced to the MMA. Polyvinyl alcohol particles are then injected to seal off this portion of the artery and prevent any further blood flow into the subdural hematoma. All catheters are then removed and hemostasis is obtained at the access site.

Patients will be followed post-procedure for 90 days to track any complications or recurrence/persistence of the subdural hematoma. Further treatment following standard of care will be offered if the patient develops worsening symptoms or presents with radiographic recurrence or persistence of the subdural hematoma.

A head CT, NIHSS, and modified Rankin Score will be repeated on the following schedule. These non-invasive procedures are detailed in the consent:

- Pre-Procedure
- 30 days (± 7) post procedure
- 90 days (± 10) post procedure

Data Points

Patient demographic data including but not limited to age, sex, race, comorbidities, previous neuro history, and relevant medical history will be gathered from Epic and Clindesk. Pre-procedure information gathered about the current admission include the use of anticoagulants, date of presentation with the SDH, size and hemisphere of SDH, neurologic presenting symptoms, head CTs, and neuro exams, including mRS and NIHSS.

Post-procedure data gathered include the time to embolization, time to follow up, procedural complications, neuro exam results, head CTs and angiography images. Date of surgery and need for surgical removal of recurrent hematoma will be documented if relevant.

The modified Rankin Score (mRS) is a well-established scale used to classify outcomes on a 0 to 6 point scale where outcome is classified as: 0- no neurological deficits, 1-no significant disability, 2- slight disability, 3-moderate disability (requires assistance with activities of daily life, but able to walk unassisted), 4-moderately severe disability (requires assistance in activities of daily life and unable to walk unassisted), 5-severe disability (bedridden, incontinent), or 6-deceased.

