The National Institutes of Health Stroke Scale (NIHSS) is an objective measure of impairment caused by a stroke. Eleven items are evaluated, with a potential score ranging from 0 to 42, with a higher score indicating more impairment.

Privacy/Data Protection

Patients will be assigned a unique study identification number at the time of consent. This number will link to identifying protected health information in a separate locked database accessible only to relevant research team members. Clinical study data will be entered into a secure database on RedCap under the study ID number to maintain patient data confidentiality.

Screening:

Study ID	MRN	Last Name	First Name	Admit Date	Enrolled Y/N	Date Consent Signed	Signed By Patient/ LAR	Exclusion

Initial Data:

Study ID	Birth Year	Sex	Race	(relevant comorbidities)	Use Anticoagulant y/n	Name of Med (aspirin, warfarin)	Procedure Date	Presenting neuro symptoms

Any neuro history	NIHSS Presentation	Baseline mRS	Size of SDH at Presentation	Laterality of SDH Left Right bilateral	Procedural Complications	

Follow up:

Study ID	Date of Follow Up	Time Point (30, 90 days)	NIHSS	mRS	Size of SDH at follow up	Neuro Deficit

Analysis

Endpoints

Two primary endpoints will be analyzed, related to the two main aims of the study. Aim 1 is to establish if middle meningeal artery embolization is more effective than observation alone at preventing recurrence of subdural hematoma. Aim 2 is to determine if adding on middle meningeal artery embolization reduces the need for further surgery in patients that initially undergo evacuation. The number of patients that experience a recurrent or refractory subdural hematoma will be compared, as well as the number of patients in each group that require surgery after undergoing embolization.

Primary Endpoints:

Recurrent or progressive SDH
Secondary surgical evacuation required

Secondary Endpoints:

Change in size of SDH at follow up
Procedure-related complications
New neuro deficit
NIHSS/mRS at follow-up intervals

Statistical Analysis

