Statistical comparisons will be made for the number of patients that experience a recurrent or refractory subdural hematoma, as well as the number of patients in each group that require evacuation surgery after undergoing embolization, an indication that the embolization procedure failed. These primary endpoints will be compared with simple t-test. The secondary endpoint of the change in the size of the subdural hematoma on radiographic imaging will be analyzed by repeated measures ANOVA. Change in score on NIH Stroke Scale pre and post embolization will be compared to determine the functional outcome of the procedure. For a safety analysis, the rate of procedure-related complications between embolized patients and surgical controls will be compared by t-test. Rankin Score at the follow up intervals will be compared with a Chi Square analysis.

Safety Monitoring Plan

Research will be performed according to protocols approved by the Institutional Review Board at Washington University in St. Louis School of Medicine. An application to the IRB is currently pending.

Patients with subdural hematoma present with symptoms including confusion or altered mental status, decreased consciousness, weakness or numbness on one side of the body, headache, seizure, and difficulty with speech, swallowing, or walking.

During this study, assessment of medical history and physical examination will be performed at baseline and at stated follow up intervals to ascertain neurologic status, change in functional baseline, and occurrence of any AEs. Prior to interventional procedures, patients have coagulation tests performed to assess risk of bleeding. If the patient has an allergy to iodinated contrast, they will receive standard pre-medication. During the embolization procedure, patients undergo continuous vital sign monitoring and are assessed frequently by a dedicated, ACLS-certified procedural nurse. The patient will be monitored as an inpatient in the neuroICU or stepdown unit for a minimum of 24-48 hours after the procedure.

Adverse Events

An adverse event (AE) is any untoward medical occurrence in a subject during participation in the clinical study or with use of the experimental agent being studied. An adverse finding can include a sign, symptom, abnormal assessment (laboratory test value, vital signs, electrocardiogram finding, etc.), or any combination of these.

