Expected risks to the subject due to the interventional procedure are minor pain and bruising at the catheter insertion site. About 5% of subjects may develop a hematoma, a collection of blood that may cause more bruising and pain than normal and may require intervention. Less likely, more serious risks of embolization procedures (<1%) include temporary neurologic deficits, blindness or cranial nerve palsy, or an anaphylactic reaction to the contrast dye.

There is a small risk (0.3%) of carotid artery dissection and/or stroke with permanent neurologic deficit from catheter injury or clot formation. Arterial perforation or brain hemorrhage is a life threatening but rare complication. Insertion site infection is exceedingly rare.

When procedures are performed through the radial artery, a combination of medications are used to prevent radial artery occlusion, which may be asymptomatic or may cause hand ischemia and the loss of the hand. Radial subjects receive a TR band at the conclusion of the procedure to maintain patent hemostasis. Radial artery occlusion is rare with these prevention measures. Femoral access subjects receive manual compression or a closure device and must be maintained on strict bedrest for 6 hours to prevent hematoma formation.

These risks are addressed in the consent form and are considered to be minimal or outweighed by the risk of multiple invasive surgical procedures or the risk to the patient by reaccumulation of the hematoma. Patients with known contraindications to angiography or comorbid conditions placing them at higher risk of procedural complications are excluded from study participation. The neurointerventional radiology department at BJH is a high volume center with experienced physicians and staff. Approximately 1200 outpatient diagnostic cerebral angiograms are performed each year and over 300 interventional procedures.

Study subjects will be followed for research purposes for 90 days and may continue long term follow up with their outpatient neurosurgeon. Study follow up visits occur at 30 days (± 7) post procedure, and 90(± 10) days post procedure. At each of these time points the subject will receive a head CT scan, neurologic assessment, and assessment of adverse events. Adherence to follow up visits will be tracked and reported.

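### Repeated measures ANOVA of hematoma size comes with no rule for missing scans or scans after rescue evacuation, and its default can mask or reverse a size benefit of embolization

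*Combined protocol and SAP*

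**What the plan says.** All references are to the combined protocol and SAP.

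- **Endpoint.** The Endpoints section lists "Change in size of SDH at follow up" as secondary. Statistical Analysis adds only this: "The secondary endpoint of the change in the size of the subdural hematoma on radiographic imaging will be analyzed by repeated measures ANOVA". It names no model terms, analysis set, missing-scan rule or rule for scans after surgery.
- **Scans.** Study Procedure sets CTs before the procedure, at 30 days (± 7) and at "90 days (± 10) post procedure". The Risks section says: "At each of these time points the subject will receive a head CT scan". Neither makes an exception after an evacuation. The windows count from the procedure, and no time origin or schedule is given for the historical controls.
- **Rescue.** Study Procedure: "Further treatment following standard of care will be offered if the patient develops worsening symptoms or presents with radiographic recurrence or persistence". Statistical Analysis calls evacuation after embolization "an indication that the embolization procedure failed", and it is a primary endpoint.
- **Surgery records.** Data Points: "Date of surgery and need for surgical removal of recurrent hematoma will be documented if relevant".
- **Rates and numbers.** Participants expects surgery for recurrent or refractory hematoma in 20% without embolization and 5% with it. It plans 200 embolized patients and 400 controls from chart review. Dropout is met by enrolling more patients; no rate is given.

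**The concern.** Two features of the named method matter here.

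First, in its classical form it needs every patient measured at every common time point, so a patient without one of the three scans leaves the analysis. One comparison group was scanned in routine care and has no stated day zero, so its complete set may be a selected one.

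Second, unless told otherwise, the method uses whatever size is on the scan. A patient whose hematoma grew and was then surgically removed has a small hematoma at day 90. The same event is a failure on the primary endpoint and an improvement on the size endpoint. The plan expects it four times as often in controls (20% against 5%), so the effect does not cancel between groups.

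Size bears on the plan's own hypotheses: resolution at 90 days in Aim 1 and radiographic improvement in Aim 2. A size result that disagrees with the surgery result could be an artefact and would be hard to interpret afterwards.

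**Working it through.** **Inputs.** The documents supply the 20% and 5% surgery rates (stated once, not by aim), 200 embolized patients and 400 controls. They give no hematoma size, SD, expected size effect or missing-scan rate, so there is no figure of the plan's to reproduce for this endpoint. The stated sample size of 124 concerns the surgery endpoint and is not used. Every millimetre, SD and missingness value below is an assumption.

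**1. Shift from post-evacuation scans.** Suppose every rescue evacuation precedes the day-90 scan, and the gap between un-evacuated and post-evacuation size is the same in both groups. Then

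shift = (0.20 − 0.05) × gap = 0.15 × gap, against embolization.

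With an assumed 15–20 mm un-evacuated and 3–8 mm after evacuation, the gap runs from 15 − 8 = 7 mm to 20 − 3 = 17 mm:

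- 0.15 × 7 = 1.05 mm
- 0.15 × 17 = 2.55 mm

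If only some evacuations precede the scan, the shift shrinks in proportion.

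**2. Against sampling error.** With an assumed SD of 6 mm, the standard error at 200 vs 400 is 6 × √(1/200 + 1/400) = 0.52 mm. The shift is then about 2.0 to 4.9 standard errors. Those totals span both aims. Each aim has fewer patients (the split is not given), so its standard error is larger and the ratio smaller.

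**3. Worked example (embolization minus control, change at day 90).** Assume −6 mm in non-failures, +4 mm in failures left alone and −10 mm in failures after evacuation (gap 14 mm).

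- Without rescue: (0.95 × −6 + 0.05 × 4) − (0.80 × −6 + 0.20 × 4) = −5.5 − (−4.0) = −1.5 mm, favouring embolization.
- Post-evacuation scans as measured: (0.95 × −6 + 0.05 × −10) − (0.80 × −6 + 0.20 × −10) = −6.2 − (−6.8) = +0.6 mm, favouring control.

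The change is 2.1 mm = 0.15 × 14. Across the assumption sets tried, differences of −1.2 to −1.95 mm became 0.0 to +1.2 mm.

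The example gives embolization no size benefit beyond avoided failures. If it also shrank non-failures by a further b mm, the as-measured difference would be 0.6 − 0.95b. This returns to favouring embolization once b exceeds 0.6/0.95 = 0.63 mm, although the 2.1 mm distortion remains and grows slightly less important.

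**4. Missing scans.** If a share m is missing independently at each follow-up visit, (1 − m)² of patients stay complete:

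- m = 10%: 0.81, or 162 of 200 and 324 of 400
- m = 20%: 0.64, or 128 of 200 and 256 of 400

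That is lost precision. For bias, take the no-rescue example (−1.5 mm) and delete incomplete patients:

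| Incomplete among failures | Incomplete among others | Difference (mm) |
|---|---|---|
| 20% | 20% | −1.50 |
| 40% | 10% | −1.09 |
| 50% | 10% | −0.94 |
| 80% | 10% | −0.41 |

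For the second row, embolization is (0.855 × −6 + 0.03 × 4)/0.885 = −5.66 and control is (0.72 × −6 + 0.12 × 4)/0.84 = −4.57.

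The direction depends on the pattern. With the second row reversed (10% of failures and 40% of others incomplete), embolization is (0.57 × −6 + 0.045 × 4)/0.615 = −5.27 and control is (0.48 × −6 + 0.18 × 4)/0.66 = −3.27. The difference is −2.0 mm, which exaggerates the benefit.

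**5. Simulation at 200 vs 400.** Comparing mean day-90 change, rather than fitting the full ANOVA, gave −1.50 mm without rescue or loss, +0.58 with post-evacuation scans, −1.09 with complete cases only (40% vs 10%), and +0.45 with both.

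**The case against.** The strongest reply is that the plan is silent, not wrong. A reader might infer that it states that incomplete patients are dropped and that evacuated failures are scored as improved. It states neither; both are defaults of the classical method applied to the scheduled scans.

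Three further inferences also fail:

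- **That deletion in itself biases the result.** It does so only if missingness is related to outcome in a way that alters the group contrast. The first row of the table shows no bias.
- **That control CTs will rarely fall in the windows.** No section says how often controls were scanned. What can be said is that no schedule or time origin is stated for them.
- **That controls will come out ahead on size.** The 1.05–2.55 mm is a shift, not a predicted result. It reverses the sign only if it exceeds the true benefit, which the documents do not quantify.

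Size regardless of later surgery is also a legitimate treatment-policy target. This matters most in Aim 2, where repeat surgery is part of the historical comparator and Group 2 has evacuation by design. A blanket exclusion of post-evacuation scans would be wrong there.

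Finally, the endpoint is secondary, evacuation is counted separately as a primary endpoint, and the rescue shift works against embolization, so it does not manufacture a claim of benefit.

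All of this limits the point. What stands is that no target is declared, and that the named method is a poor default when rescue is expected to be unequal and one group's scan timing is undefined.

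**Conclusion.** The point holds as a recommended change, not a fatal flaw. Used in its classical form, the named analysis loses patients without all three scans. By default it also reads rescue evacuation as hematoma shrinkage, unequally by group. The second effect is the more certain. It follows from the plan's own 20% and 5% and equals 0.15 times the size gap, or 1.05–2.55 mm for an assumed 7–17 mm. This is enough to mask or reverse a modest benefit on this endpoint.

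The formula assumes that evacuations precede the day-90 scan and that the gap is equal between groups. The size of the missing-scan effect, and whether it is bias or only lost precision, cannot be settled from the documents. As-observed size need not be abandoned, but it should be a declared target and not the only analysis.

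**What to change.** 1. Replace repeated measures ANOVA with a linear mixed model on all available scans, with group, visit, group × visit, baseline size and actual scan day, run separately for each aim.
2. State day zero for the controls and how their CTs map to the 30- and 90-day visits.
3. State the target for unplanned evacuation after the index treatment. Keep Group 2's planned evacuation outside this rule, and say how repeat surgery is treated where it is part of the Aim 2 comparator.
4. Report two analyses side by side: sizes as observed, and one in which scans after unplanned evacuation do not count as improvement. For the second, either exclude those scans from the mixed model or run a separate rank-based analysis that scores evacuation as failure. Exclusion assumes that earlier scans predict what the size would have been, so say so. Worst-rank scores do not belong inside the linear model.

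**Cost.** One rule fixed in advance and one extra sensitivity analysis. Surgery dates are already to be recorded, so post-evacuation scans can be identified. Control CT dates must be abstracted with the sizes, a modest addition to the chart review if not already intended.

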From recent meta-analysis, three dual-armed studies that compared embolization and conventional surgery groups and six single-armed case series were identified and analyzed. Hematoma recurrence rate was significantly lower in the embolization group compared to the conventional treatment group (2.1% vs 27.7%, OR .087, 95% CI .026-.292, $p<.001$, $I^2=0\%$), whereas surgical complication rates were similar between the two (2.1% vs 4.4%, OR 0.563, 95% CI 0.107-2.96, $p=.497$, $I^2=27.5\%$). Number of patients with mRS>2 in the embolization (12.5%) versus conventional treatment (9.1%) groups also showed no statistical difference ($p=.689$). A composite hematoma recurrence rate of 3.6% was found after summing the six-case series. Composite recurrence and complication rates in the embolization cohorts of the dual-armed studies as well as the case series were also lower than literature values for conventional surgical treatments. Since then, there has been one study with 60 embolizations showing a 90% success rate of avoiding subsequent surgery with no procedural-related complications.

Objective

Through the use of a prospective dual cohort, this study seeks to assess the safety and efficacy of middle meningeal artery embolization for subdural hematoma in addition to standard treatments, which include observation and surgical evacuation. Middle meningeal artery embolization has emerged recently as a minimally invasive and successful method of preventing re-accumulation of subdural hematoma, particularly for patients that are not obvious surgical candidates or those with recurrent or refractory hematomas. We will compare the outcomes of these two groups of patients who undergo middle meningeal artery embolization to matched historical controls from the past four years.

Specific Aim 1:

Determine the efficacy of middle meningeal artery embolization vs observation alone

The recurrence rate of patients that undergo the middle meningeal artery procedure will be compared to a number of medically managed patients that experience a clinically significant persistent or recurrent hematoma. This endpoint will be determined through a series of neurologic assessments and follow up imaging. Patients will be followed for 90 days.

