information gathered, time frame of participation, potential benefits, and risks of participation, including the risks of undergoing an interventional neuroradiology procedure. Treatment with middle meningeal artery embolization will be offered in addition to the standard surgical evacuation or observation by the physician in consideration of the patient's medical history and current condition. If patients are unable to provide informed consent, consent from the next of kin will be obtained in accordance with Missouri Statute Title XXVII, Section 431.064.

Patients will have as much time as they desire to think about the study, ask questions, and discuss with family. Any patient requiring emergent intervention or experiencing sudden neurologic deterioration is excluded from this study. The consent documentation contains a statement that consent is freely given, that the patient understands the potential risks and benefits of entering the study, and that the patient is free to withdraw from the study at any time. As the patient may experience a direct benefit from the study, the patient must initial yes/no to permission for future use of their data per policy. Patients who agree will then sign the IRB approved consent form prior to undergoing the procedure. The original signed consent will be maintained in a binder in a locked office. A copy will be given to the patient, with contact numbers if the patient has further questions or wishes to withdraw their consent. The expected duration of patient participation in the study is 90 days.

Based on a review of prior literature, we expect an effect size of 20% patients to meet the endpoint of recurrent or refractory subdural hematoma requiring surgery. With the addition of MMA embolization, we expect that only 5% of patients will meet this outcome. With equal numbers of patients in each arm, we estimate that 124 patients will be needed for a power of 80% using a two tailed alpha set at 0.5. In order to account for study dropout, we plan to study 200 patients who undergo MMA embolization. These patients will be compared to an additional 400 historical matched controls obtained via retrospective chart review from January 1st 2014 to December 31st 2018.

Inclusion/Exclusion Criteria

Must meet the following criteria for inclusion to undergo MMA embolization:

1. Patients 18 years or older undergoing treatment for a new diagnosis of chronic or acute subdural hematoma (cSDH)
or

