Patients 18 years or older who have undergone surgical evacuation of a subdural hematoma and have a significant residual hematoma status post-surgery or who develop a recurrent subdural hematoma.
2. Minimal symptoms such as headache, altered mental status, or mild neurological deficit only
3. Ability to understand and sign written informed consent by patient or LAR

If any of the following criteria are met, the individual will be excluded from participation:

1. Significant midline shift and/or neurologic symptoms requiring urgent decompression.
2. Common carotid stenosis of over 50%.
3. Significant contraindication to angiography (eg. kidney failure, difficult anatomy).

4. SDH related to underlying condition

Groups:

1. Embolization Only
 - a. Patients with new chronic or acute SDH with minimal symptoms only, or who are poor surgical candidates (dual antiplatelet therapy or systemic anticoagulation, ASA Class 4 or greater)
2. Embolization + Standard of Care Evacuation
 - a. Patients with chronic or acute SDH who failed conventional surgery at any point needing additional intervention, not requiring urgent evacuation
 - b. Recurrent SDH
3. Medical Management (Historical Cohort)
4. Surgery Alone (Historical Cohort)

Study Procedure

Middle meningeal artery embolization is ideal for patients with minimal symptoms or that are poor surgical candidates due to the need for continued anticoagulant or antiplatelet therapy. For patients who meet inclusion criteria, MMA embolization as an adjunct treatment will be offered. For patients that are medically managed, they will undergo MMA embolization to prevent growth or recurrence of the hematoma and have standard imaging follow up. For patients that require evacuation of the hematoma due to size or symptoms, they will undergo standard of care surgery via burr hole or craniotomy at the treating neurosurgeon's discretion and then at a later date during the same hospitalization receive MMA embolization. These patients may have already had multiple surgical evacuations with recurrence of the hematoma.

Once consented and enrolled, patients will undergo MMA embolization in the neuro-angiography suite via selective MMA catheterization and embolization with 150-250 micron polyvinyl alcohol (PVA) particles. The neurointerventional radiology department at BJH is a high volume center. Physicians and staff are experienced in neurovascular embolization for a variety of indications.

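### NIHSS is analysed as a before-after change with no control comparison named, and the mRS chi-square uses neither the order of the scale nor the baseline score (secondary endpoints only)

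*Combined protocol and SAP*

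**What the plan says.** The Statistical Analysis section gives one sentence to each functional scale.

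- NIHSS: "Change in score on NIH Stroke Scale pre and post embolization will be compared to determine the functional outcome of the procedure". No comparator, test or time point is given.
- mRS: "Rankin Score at the follow up intervals will be compared with a Chi Square analysis". No cut-point, trend version or covariate is given.
- The same paragraph does name a comparator for safety: "the rate of procedure-related complications between embolized patients and surgical controls will be compared by t-test".

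Elsewhere in the protocol:

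- The Objective states the general design: "We will compare the outcomes of these two groups of patients who undergo middle meningeal artery embolization to matched historical controls".
- Participants gives the source of the controls: "400 historical matched controls obtained via retrospective chart review from January 1st 2014 to December 31st 2018". The matching variables are not listed.
- Secondary Endpoints lists NIHSS and mRS at the follow-up intervals, that is, as levels and not as changes.
- Study Procedure schedules NIHSS and mRS before the procedure, at 30 days and at "90 days (± 10) post procedure".
- Patients who need evacuation have surgery first and then "at a later date during the same hospitalization receive MMA embolization".
- The Initial Data form has a Baseline mRS field and an NIHSS Presentation field. It has no field labelled as pre-procedure NIHSS.
- mRS is defined as 0 to 6 with 6 for death. NIHSS is defined as 0 to 42, with no value for death.

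**The concern.** The NIHSS sentence says that the change is meant to show the functional outcome of the procedure. A change measured only in embolised patients mixes three things: any effect of embolization, ordinary recovery over 90 days, and, in Group 2, recovery from the evacuation. A favourable change could then be reported as a result of embolization when there is none.

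For mRS the risk is different. A Pearson chi-square on seven levels treats them as unordered and takes no account of where patients started. It is less likely to pick up a consistent shift in disability, whether benefit or harm. With historical controls and unnamed matching variables, it also offers no protection if the groups differ in baseline mRS.

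**Working it through.** The documents give no effect size, SD or power for NIHSS or mRS, so there is no stated figure to reproduce. The check is a reading of the text plus illustrations on assumed inputs.

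**1. Reading the NIHSS plan**

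- *Literal reading (embolised patients only).* Controls were not embolised, so a pre/post embolization pair is not defined for them and nothing removes background recovery. For Group 2 the size of the problem depends on which score is the pre value. If it is the NIHSS Presentation field, evacuation lies between pre and post and its benefit is counted in the change. If it is the pre-procedure score, that part is reduced, but recovery continuing after surgery remains.
- *Between-group reading.* Follow-up days are counted post procedure, and no equivalent date is defined for controls. No control baseline is defined. A patient who dies has no NIHSS value, and no rule is given.

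**2. How often background recovery alone would be significant**

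Assumptions: no embolization effect, mean improvement d = 0.5 point from other causes, SD of change 3, a paired t-test (the plan names no test), two-sided 0.05. The number embolised is 200 in the protocol; 100 per aim is an assumed even split.

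Noncentrality = (d/SD) × √n.

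- n=100: (0.5/3) × 10 = 1.667, critical t 1.984: significant in 38% of trials.
- n=200: (0.5/3) × 14.14 = 2.357, critical t 1.972: significant in 65%.
- SD 4 to SD 2: 24% to 70% at n=100, and 42% to 94% at n=200.
- d = 0.25, SD 3: 13% and 22%.

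**3. mRS: power lost by ignoring order**

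Assumptions: control mix for mRS 0-6 of 40/30/20.9/4/2.5/1/1.6%. The upper part sums to 4 + 2.5 + 1 + 1.6 = 9.1%, set to the conventional-treatment rate of mRS>2 in Prior Research. The rest of the mix is assumed. The embolised mix comes from a common odds ratio (OR): odds(mRS ≤ k) in embolised = OR × odds(mRS ≤ k) in controls. For example, at OR 1.5 the share at mRS 0 goes from 0.40 (odds 0.667) to odds 1.0, that is 0.50. Groups are 100 vs 200 (half of 200 and 400, assumed). Power is by simulation, two-sided 0.05.

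| OR | chi-square, 7×2 | chi-square, levels 3-6 collapsed | rank (Wilcoxon) test |
|---|---|---|---|
| 1.5 | about 17% | about 28% | about 44% |
| 2.0 | about 52% | about 69% | about 84% |

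The collapsed column matters because the upper levels are sparse. In 100 patients with the control mix, levels 3 to 6 have expected counts of 4, 2.5, 1 and 1.6, so an analyst might well merge them. With no effect and balanced groups, the 7×2 chi-square rejects in 4-5% of trials, so it is valid.

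**4. mRS: order without baseline is not a cure**

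Assumptions: no effect; baseline mRS 0-4 in controls at 25/30/25/12/8% (mean 1.48); 0.8 log-odds of worse follow-up mRS per baseline point; embolised patients better at baseline; 100 vs 200.

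| embolised baseline mean | chi-square | unadjusted rank test | baseline-adjusted rank test |
|---|---|---|---|
| 1.22 | 5% | 13% | 4-5% |
| 1.04 | 10% | 30% | 4-5% |

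The entries are false-positive rates. The unadjusted rank test is hurt more by imbalance than the chi-square, so the adjustment is needed as well as the ordering.

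**The case against.** The single-arm reading of NIHSS is not forced. The Objective promises comparison of outcomes with matched historical controls. The Statistical Analysis section also uses embolization loosely as a time marker: it counts surgery after embolization in each group, although controls had none. The mRS sentence names no comparator either. A reader might infer that the plan has decided on an uncontrolled NIHSS analysis. The documents do not support that; they show only that no control comparison is specified. This stands, and it limits the point. The gap remains on the between-group reading, because controls have no time zero.

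A significant before-after change is a correct finding if patients did improve; it misleads only when credited to embolization. That also stands, but the sentence says the change will determine the functional outcome of the procedure, which invites that credit. The 38% and 65% rest on an assumed test, recovery and SD, and the range is wide.

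On mRS, a reader might infer that chi-square is an invalid test here. It is not: with balanced groups its error rate is correct. A trend version or a prespecified cut-point would be an ordinary use, but neither is stated. The mRS>2 split in Prior Research describes a cited meta-analysis and is not adopted for this study. Collapsing sparse levels narrows the power gap without closing it.

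Lack of a control time zero and of matching variables is a general weakness of the historical-control design. That is true, but the functional analyses cannot be run between groups without settling it.

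**Conclusion.** The concern holds in a limited form. As written, the NIHSS analysis names no control comparison and cannot by itself support a statement about the effect of embolization. The mRS chi-square is valid with balanced groups but inefficient, and balance on baseline mRS is not assured because the matching variables are unnamed.

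Only secondary endpoints are affected, and the primary conclusions do not change. The percentages illustrate the direction and rough scale of the problem; they do not predict this trial's results. Apart from the 9.1% rate and the totals of 200 and 400, their inputs are assumed. The only mRS comparison in the documents runs the other way and is not significant: "Number of patients with mRS>2 in the embolization (12.5%) versus conventional treatment (9.1%) groups also showed no statistical difference" (p=.689). Odds ratios of 1.5 and 2.0 therefore should not be read as expected benefits.

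The change is worth making because it is cheap and uses controls already planned and a baseline already collected. Confidence is medium, since a controlled NIHSS comparison may have been intended.

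**What to change.** 1. **NIHSS.** Compare follow-up NIHSS in each embolised cohort with its own matched controls, adjusted for baseline NIHSS (ANCOVA, or rank ANCOVA with death ranked worst). Define baseline and time zero the same way in both groups. For Group 2 and its surgical controls, take the baseline after evacuation in both. Count 30 and 90 days from that time zero. If control charts lack these scores, report the before-after change as descriptive and draw no conclusion about the effect of embolization.
2. **mRS.** Replace the chi-square with an ordinal between-group analysis at 30 and 90 days (proportional odds or a rank method, death as level 6), adjusted for baseline mRS and for the matching variables, which must be named. Do not substitute an unadjusted ordinal test. If control baseline mRS is unavailable, report the comparison as descriptive.
3. **Form.** Reconcile the pre-procedure NIHSS scheduled in Study Procedure with the NIHSS Presentation field on the Initial Data form.

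The cost is revised analysis wording and programming, one form label, and a check of the 2014-2018 charts for baseline and follow-up scores and a usable time zero. The documents do not say what those charts contain, and this decides between a comparison and a description. Two limits remain: the proportional-odds assumption if that model is used, and historical-control confounding that adjustment does not remove.
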